1 BACKGROUND INFORMATION

1.1 Introduction

Pain is the most common symptom for which subjects seek medical attention, but pain management has unmet needs. Pain is the most frequent reason why subjects visit an emergency department and there is a need for additional research on the relative safety and efficacy of non-opioid approaches to emergency department analgesia (Todd, 2017). Chronic pain affects between one-third and one-half of the population of the United Kingdom (UK), corresponding to just under 28 million adults and is likely to increase due to an ageing population (Fayaz et al., 2016).

Pain is defined by the International Association for the Study of Pain as: "*An unpleasant sensory and emotional experience associated with actual or potential tissue damage or described in terms of such damage*" (www.iasp-pain.org). Pain is subjective and this definition links emotion and past experience to the sensory event thus also highlighting that pain is a complex experience that includes multiple dimensions. This is because each individual learns the meaning of the word "pain" through experiences related to injury in early life. Stimuli or illnesses that cause pain are likely to damage tissue and hence pain is an experience associated with actual or potential tissue damage. Pain is almost always unpleasant and therefore an emotional experience. Pain is subjective and there are no satisfactory objective measures of pain, hence the subject's self report of pain is the most reliable indicator of pain (American Pain Society, 2006).

Clostridial neurotoxins from the botulinum neurotoxin (BTX) family are protein complexes, derived from the bacterium *Clostridium botulinum*, which potently inhibit acetylcholine release and results in a reversible blockade of the neuromuscular junction. This feature led to the clinical development of BTX for neuromuscular disorders. Serotype A BTX (BTX-A) are commercially available and clinically used for treatment of disorders characterised by increased tonicity or overactivity of specific muscles (Barnes, 2003; Thenganatt et al., 2012), and also for treatment of overactivity of secretory glands (Heckman et al., 2001). Along with the neuromuscular effect, it has been reported that BTX-A reduces the pain associated with the neuromuscular hyperactivity disorders, such as torticollis (Tsui et al., 1985; Brin et al., 1987; Tarsy, 1999).

BTX-mediated pain relief was initially described in conditions associated with muscle contraction and believed to be associated with decreased contraction of affected muscles (Arezzo, 2002; Cohen et al., 1989; Mense, 2004). It was proposed that BTX-A, by inhibiting the release of acetylcholine in hyper-functional muscular end plates, may indirectly prevent the painful ischaemia caused by muscle contractures in spasticity and dystonia (Mense, 2004). However, it was reported that the observed pain relief in patients treated for spasmotic torticollis was not concurrent with neuromuscular effects since it was present in some patients even when dystonic posture of the neck was not improved (Stell et al., 1988). Additionally, BTX-A-mediated pain relief does not always occur simultaneously with the observed paralytic effect in focal dystonias, and it sometimes even persists after the neuromuscular benefit is no longer visible (Aoki, 2003; Freund, 2003). Since the onset of BTX-A action on pain did not correspond to the onset of paralytic muscular effects or lasted longer than the paralysis, toxin action on sensory or vegetative nerves was suggested (Giladi, 1997; Mense, 2004).

Independently from pain which might be related to increased muscle contraction, the anti-nociceptive effect of BTX-A was also reported in different types of chronic pain not associated primarily with muscle hyperactivity, such as migraine (Silberstein et al., 2000; Luvisetto et al., 2015) and different types of neuropathic pain (Argoff, 2002; Attal et al., 2016).

Along with experimental knowledge obtained from preclinical studies, it is now accepted that BTX-A effects on pain may be mediated by its direct effects on sensory nerves, and current

evidence suggests several possible peripheral nervous system and central nervous system mechanisms of action, which might account for the analgesic action of peripherally administered BTX-A across the whole nociceptive pathway (Pellett et al., 2015):

- BTX-A acts on neurons involved in pain perception and prevents the release of other neurotransmitters than acetylcholine, e.g. glutamate, substance P, calcitonin gene-related protein (CGRP) and vasopressin as demonstrated in vitro from cultured cells or isolated materials (Mc Mahon et al., 1992; Purkiss et al., 2000) and also in vivo in preclinical pain models, e.g. in the rat formalin test (Cui, 2004) or the rat capsaicin pain model (Bach-Rojecky, 2005; Filipovic et al., 2012; Marino et al., 2014),
- BTX-A may regulate the expression of a variety of receptors and channels implicated in peripheral sensitisation, amongst which vanilloid receptors such as the transient receptor potential vanilloid 1 (TRPV1) (Apostolidis et al., 2005) whose mobilisation from intracellular stores to the plasma membrane involves regulated exocytosis (Dolly et al., 2009) and cleavage of the synaptosomal-associated protein 25 (SNAP-25) (de Paiva et al., 1993),
- Following endocytosis in the peripheral terminals, some molecules of BTX-A may undergo retrograde transport along the axon and reach the dorsal root ganglion (DRG) neurons where they would block the vesicular release of neurotransmitters into the extracellular milieu of the DRG, which would otherwise activate and excite the neighbouring sensory neurons (Dickenson, 1987a; Matak et al., 2012),
- Though speculative, BTX-A may also further undergo intra-vesicular trafficking to the central terminals, and block neurotransmission into the brainstem and higher centres for pain integration (Coderre et al., 1990; Dickenson, 1987b).

Dysport® is the trade name for an injectable form of BTX-A, which is isolated and purified from the bacterium *Clostridium botulinum*. Dysport was first registered for the treatment of blepharospasm and hemifacial spasm in the UK in 1990. It is licensed in more than 85 countries for various indications including: spastic equinus foot deformity due to spasticity in adults following a stroke, blepharospasm, adult upper and lower limb spasticity, hemifacial spasm, spasmodic torticollis (also known as cervical dystonia), paediatric lower limb spasticity and dynamic equinus foot deformity due to cerebral palsy, axillary hyperhidrosis, and glabellar lines.

The present study will investigate the analgesic effects of different doses of Dysport in subjects experiencing chronic pain from an abdominal or thoracic scar (chronic post-surgical pain; post-surgical neuralgia).

1.2 Name and Description of the Investigational Medicinal Product

Dysport is formulated as a complex of BTX-A with haemagglutinin (BTX-A-HAC), a large therapeutically inert protein used to stabilise the toxin. Dysport is formulated with lactose (bulking agent) and human serum albumin, and is supplied as a lyophilised powder.

A detailed description can be found in the Summary of Product Characteristics (SmPC).

1.3 Non-Clinical Data

The analgesic properties of commercially available BTX-A have been investigated in a variety of acute and chronic animal pain models. The effectiveness of BTX-A has specifically been demonstrated in formalin- (Cui, 2004; Luvisetto et al., 2006) and capsaicin-induced pain models (Marino et al., 2014; Ramachandran et al., 2015), as well as in arthritic rats (Krug et al., 2009) and dogs (Heikkila et al., 2014). Positive outcome following

administration of BTX-A has also been evidenced in mononeuropathy (peripheral and infraorbital nerve ligation, ventral root transection), polyneuropathy (chemotherapy-induced, diabetes) and trigeminal murine pain models ([Favre-Guilbard et al., 2009](#); [Bach-Rojecky et al., 2010](#); [Gazerani et al., 2010](#); [Filipovic et al., 2012](#); [Shimizu et al., 2012](#); [Park et al., 2015](#)).

1.4 Clinical Data

Botulinum toxin injection is being increasingly used “off-label” in the clinical management of chronic pain, and there have been a number of reviews highlighting the role of treating painful conditions with BTX. In their review of BTX in the treatment of chronic pain, [Rivera Dia et al. \(2014\)](#) discuss several conditions where BTX may have a role, such as trigeminal neuralgia, tension headache, chronic migraine, myofascial pain, phantom limb pain and joint pain. [Park and Park \(2017\)](#) also reviewed the experimental and clinical evidence of the mechanism by which BTX acts on various types of neuropathic pain. They described how BTX can be applied as treatment for neuropathic pain conditions such as postherpetic neuralgia, post-surgical neuralgia, diabetic neuropathy, occipital neuralgia or spinal cord injury induced neuropathic pain. They also provide clear evidence that BTX has an analgesic effect involving both peripheral and central elements of the nociceptive pathway for chronic neuropathic and nociceptive pain.

Besides use for aesthetic treatments and infocal hyperhidrosis, BTX has also been recently used experimentally in many other dermatological conditions with good results. [Campanati et al. \(2017\)](#) analysed the possible BTX “off-label” applications in dermatology and specifically collected published data on the application of BTX-A injections in keloids and hypertrophic scars. The studies reviewed revealed a great potential for BTX-A with improvement of the lesions such as lowering of the erythema, decrease of the itching, pain and tenderness sensation, but also decrease in size and flattening of the lesions. Overall, the therapeutic satisfaction of the patient and physician was good in the studies reviewed.

Of relevance for the present study, [Schwartz et al. \(2004\)](#) investigated the effects of intradermal injections of BTX-A in relieving chronic post-surgical scar pain. They showed that subjects treated with BTX-A exhibited an improved reduction in mean pain scores relative to dexamethasone (30% versus 25%) and twice the duration of effect (eight weeks for BTX-A versus four weeks for dexamethasone).

1.5 Rationale for the Study

The rationale of this study is to test the hypothesis that Dysport is effective in relieving chronic scar pain when administered intradermally. This study will also aim at characterising the pharmacodynamic profile of any analgesic effect of a predefined dose range (time to onset, peak-effect, time to peak-effect and duration of effect).

1.6 Dosage Selection

[figure not shown]
The anhidrotic properties of a range of single intradermal 0.2 mL doses of Dysport (2.5, 10 and 20 U) were studied in healthy volunteers ([Ipsen Study CCI](#)). These doses were well tolerated and showed a dose-related increase in the anhidrotic area using the Minor's starch-iodine test. The maximal mean areas were 1.1, 2.7 and 3.7 cm² (corresponding radius of 0.6, 0.9 and 1.1 cm) for 2.5, 10 and 20 U respectively.

Those same dose levels of 2.5, 10 and 20 U and route of administration have been selected for the individual injection points in the present study.

The minimal dose will be 2.5 U injected in four sites (i.e. total dose of 10 U).

The maximal diffusion radius (1.1 cm for Dysport 20 U), together with the specification related to the maximal length of the pain area (i.e. no more than 10 cm) have been taken into consideration for the injection paradigm where individual injection points will be given intradermally 2 cm apart and the maximal number of injection points limited to 10 (see Figure 1). The maximal allowed total dose in the present study will thus be 200 U in the Dysport maximal dose group (20 U), which is consistent with the maximal recommended intradermal dose in the product label.

Figure 1 Injection Paradigm

1.7 Population to be Studied

This study will enrol male and female subjects with a painful abdominal or thoracic scar. Pain should be rated as moderate to severe i.e. numerical rating scale (NRS) score between 4 and 8 on an 11-point scale (0-10), and stable within one month before screening. The pain should also be chronic, i.e. persistent for more than six months after the surgery which led to the painful scar.

To ensure subjects will potentially benefit from intradermal injection of Dysport, they will be tested for responsiveness to local anaesthetic (lidocaine) during a pre-randomisation run-in period. This is consistent with use of diagnostic local anaesthetic blocks which are used to obtain information about of the source of subject's pain, being target specific and controlled in order to exclude false positive results (Bogduk, 2002). This assessment will be performed by investigators with experience in managing subjects with painful conditions and pain studies.

1.8 Known and Potential Risks to Human Subjects

Dysport is licensed in the UK for the symptomatic treatment of focal spasticity, spasmotic torticollis, blepharospasm and hemifacial spasm, injected either intramuscularly or subcutaneously targeting the affected muscles or muscle groups, and is also licensed for treatment of severe primary hyperhidrosis of the axillae, injected intradermally.

Side effects of Dysport as experienced with intradermal injection for hyperhidrosis indication were local injection site reactions including pain, bruising, pruritis, and oedema. In addition, rash and compensatory sweating were also reported.

The maximum licensed intradermal dose is 200 U per area of injections. This maximum recommended intradermal dose will not be exceeded in the present study. Additional information regarding risks to human subjects may be found in the SmPC.

Overall, the safety profile of Dysport is well established after more than 20 years of clinical trials and post-marketing experience in various therapeutic and aesthetic indications at various doses with maximum dose used for intradermal indication up to 200 U at single area of injections. In the current proposed study in subjects with chronic scar pain, we believe the risk associated with Dysport use intradermally, to be acceptable, considering the established and known safety profile with intradermal use.

2 STUDY OBJECTIVES

2.1 Primary Objective

- To describe the pharmacodynamic analgesic profile (time of onset of meaningful analgesic effect, peak-effect, time to peak-effect, duration of effect) of intradermal doses of Dysport in subjects with abdominal or thoracic chronic scar pain.

2.2 Secondary Objectives

- To compare the efficacy of intradermal doses of Dysport to placebo.
- To assess the safety and tolerability of a range of intradermal doses of Dysport.

2.3 Exploratory Objectives

- To explore improvement of quality of life (QoL) using SF-36 questionnaire.
- To explore concomitant use of rescue medication (analgesia).

3 INVESTIGATIONAL PLAN

3.1 Overall Study Design and Plan

The study will consist of two sequential parts, the first being to identify subjects who will potentially benefit from intradermal Dysport injection, 'responders', who will then progress to the second part, which is the double-blind study of the intradermal injection of Dysport or placebo:

- Part A: A double-blind, randomised, initial two-period cross-over run-in part, extended screening period of placebo or local anaesthetic (lidocaine),
- Part B: A single-dose, double-blind, randomised, parallel part with one of the three different doses of Dysport or placebo.

To ensure subjects will potentially benefit from intradermal injection of Dysport, they will be tested for responsiveness to local anaesthetic (lidocaine).

In Part A, and upon consent and successful screening of medical eligibility, subjects will be injected (injection test 1) during a pre-randomisation run-in period in a double blind fashion with either saline or local anaesthetic (lidocaine) and assessed for pain perception up to 24 hours post-injection. One week later, they will be crossed over, injected with the other agent (injection test 2) and assessed for pain perception up to 24 hours post-injection. Pain intensity will be scored using a 11-point NRS (from score 0 for "no pain" up to 10 for "worst possible pain").

If subjects are assessed as responders, they will enter in Part B, and will be trained and provided with an Actiwatch® to enable them to record twice a day their spontaneous NRS scores.

[figure not shown]
Before dosing on Day 1, the subjects will perform baseline assessments including a quantitative sensory testing (QST) assessing allodynia, hyperalgesia and conditioned pain modulation, completion of a QoL questionnaire, and safety assessments (physical examination, vital signs measurements, collection of adverse events (AEs) and recording of concomitant medication).

Subjects will be dosed if considered as consistent in pain perception from the screening visit (i.e. variability < 2 for the average spontaneous NRS score pre-injection tests in Part A, pre-QST and pre-dosing and as clinically plausible per investigator's judgement).

Subjects will then be assessed for pharmacodynamics and safety for a total of 16 weeks post-dose.

Subjects will be discharged from the study after safety assessments (physical examination, vital signs) during an end of study (EoS) visit.

The study design is presented in [Figure 2](#).

Figure 2 Study Design

3.2 Study Endpoints

3.2.1 Primary Endpoints

The primary endpoints will be:

- Time to onset, i.e. time to decrease from baseline of two points in the spontaneous NRS score,
- Peak-effect, i.e. maximal decrease from baseline in the spontaneous NRS score,
- Time to peak-effect, i.e. time to reach the peak-effect,
- Duration of effect, i.e. duration between time to onset and last timepoint for which change from baseline in the spontaneous NRS score is \geq two points.

3.2.2 Secondary Endpoints

The following secondary endpoints will be evaluated:

- Change from baseline in the spontaneous NRS score to each scheduled timepoint,
- Change from baseline in the stimulus-evoked NRS score to each scheduled timepoint,
- Safety of three intradermal doses of Dysport. Safety assessments will include monitoring of AEs, concomitant medications and changes from baseline in physical examinations findings including the examination of the scar at the injection sites and vital signs recordings at each scheduled timepoint.

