9.1.3 Spontaneous Average and Worst Pain NRS Score in Part B

If subjects are responders, they will be provided with an Actiwatch® during an Actiwatch® training visit to record their spontaneous NRS score at home. They will start NRS score recording from the training visit on Actiwatch® use.

The Actiwatch® will alarm and alert the subjects twice a day to record their average and maximal NRS scores over the preceding 12 hours. The questions will be asked of the subject by the Actiwatch®:

“Please rate your pain by selecting the one number that best describes your pain on average during the last 12 hours.”

“Please rate your pain by selecting the one number that best describes your pain at its worst during the last 12 hours.”

The Actiwatch® will allow electronic NRS score collection and storage from the Actiwatch® training to EoS. Data will be extracted from the Actiwatch® at each visit. A paper diary will also be provided to subjects in the unlikely event of an Actiwatch® malfunction during the collection period. One week before post-dosing visit to the CRU, the subjects might be requested to complete the paper diary as a quality control check for the data in the Actiwatch® and as a back up in case there is a problem with downloading information from the Actiwatch®.

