		Peak-effect, i. e. maximal decrease from baseline in the spontaneous NRS score.	The mean peak in each treatment group.	
		Time to peak-effect, i.e. time to reach the peak-effect.	The mean time to reach the peak-effect in each treatment group.	
		Duration of effect, i.e. duration between time to onset and last timepoint with change from baseline in the spontaneous NRS score is ≥ 2 points.	The mean duration of effect in each treatment group (for the subjects who reach the time to onset).	

Only descriptive statistics will be provided. No statistical test will be performed.

As described in the above table, the estimand will be based on "treatment policy" strategy, which is the estimate of the treatment effect regardless of whether the subject has an intercurrent event during the study.

The following potential intercurrent events will be considered:

- The short-term use of rescue medication,
- The change in use of rescue medication.

Supplementary and sensitivity analysis will be performed to take into account these intercurrent events and to handle missing data. These analysis will be detailed in the SAP.

Analysis of the secondary endpoints

Endpoints have been defined to meet the study secondary objectives. They are presented in [Table 4](#) with their associated estimate and estimand.

Table 4 Secondary Objectives - Analysis of Secondary Endpoints

Objective	Assessments	Endpoints	Estimate of treatment effect	Estimand
To compare the efficacy of intradermal doses of Dysport to placebo.	Spontaneous pain as assessed by the spontaneous NRS score.	Change from baseline in the spontaneous NRS score to each scheduled timepoint.	Difference between each Dysport doses and the placebo group, in the mean change from baseline in the spontaneous NRS score to each scheduled timepoint.	For each estimate, the associated estimand will be based on "treatment policy" strategy (i.e. regardless of the intake of rescue medication).
	Stimulus-evoked pain as assessed by the NRS score during QST.	Change from baseline in the stimulus-evoked NRS score to each scheduled timepoint.	Difference between each Dysport doses and the placebo group, in the mean change from baseline in the stimulus-evoked NRS score to each scheduled timepoint.	For each estimate, the associated estimand will be based on "treatment policy" strategy (i.e. regardless of the intake of rescue medication).
To assess the safety and tolerability of a range of intradermal doses of Dysport	Refer to Section 11.3.1 .			

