5.1 General Considerations

All statistical analyses will be performed using the SAS® software version 9.4 or higher.

For Part A, only listings will be provided. For Part B, tables, figures and listings will be provided.

5.1.1 *Outputs Presentation*

5.1.1.1 *Tables Header*

Depending on the type of data, the summary tables will be presented as follows:

- For disposition, demographic data and baseline data description: by treatment group and overall,
- For efficacy and safety data: by treatment group and all Dysport.

5.1.1.2 *Presentation of Treatment Group*

For Part A, listings will be displayed using the following treatment group labels, in the order presented:

Long label	Short label
Lidocaine 2.5mg/injection site	Lidocaine
Placebo	Pbo

For Part B, Tables, Figures and Listings (TFLs) will be displayed using the following treatment group labels, in the order presented:

Long label	Short label
Placebo	Pbo
Dysport 2.5U/Injection site	Dysport 2.5U*
Dysport 10U/Injection site	Dysport 10U*
Dysport 20U/Injection site	Dysport 20U*

* Per injection site

When specified, tables will also be described by total dose received in the painful injection area and the total dose received in the painful area divided by the painful area.

5.1.1.3 *Presentation of Visits / Timepoints*

Summaries by visit will be presented using visit number as collected in the electronic Case Report Form (eCRF).

Visits in the TFLs will be presented as follows and in that order:

Part	Long Visit Name	Short Name
	Screening	Scr
Part A	Injection test 1 (Day -21 max)	Inj1
	Injection test 2 (Day -14 max)	Inj2
Part B	Baseline (Day -7 Day -1)	Bsl
	Day 1 Pre-dose	D1 Pre-dose
	Day 1 Post-dose	D1 Post-dose
	Day 2 Day 7	D2 D7
	Week 2	W2
	Week 4	W4
	Week 6	W6
	Week 8	W8
	Week 10	W10
	Week 12	W12
	Week 14	W14
	End of Study	EOS

5.1.2 *Descriptive Statistics*

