All raw and derived variables will be listed and described using summary statistics. For categorical variables, summary statistics will be displayed using descriptive statistics by frequency count and percentages by category. The missing category will be presented if there is one missing category for at least one treatment group. Except otherwise specified, subjects with missing data will not be included in the calculation of percentages. For quantitative variables, summary statistics will be displayed using descriptive statistics by number of observations, mean, standard deviation (SD), first quartile, median, third quartile, minimum and maximum. Missing data will be displayed.

5.1.3 *Baseline value*

Unless otherwise specified, baseline is defined as the last non-missing measurement taken within 7 days prior to IMP administration (including unscheduled assessments).

For the spontaneous NRS score, baseline will be defined as the mean of all pre-dose data (from day -7 and including pre-dose on Day 1).

5.1.4 *Reference Start Date and Study Day*

Reference start date is defined as the day of IMP administration in Part B.

The day of IMP administration will be Day 1. Study day will be calculated as:

- The difference between the event date and the reference date plus one day, if the event is on or after the reference date.
- The difference between the event date and the reference date, if the date of event is prior to the reference date.

Study day will appear in any Part B listings where an assessment date or event date appears.

In case of partial or missing event date, study day will appear missing while any associated durations will be presented based on the imputations described in appendix A3.

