- Population: Subjects in the randomised population
- Assessments: Described in table below
- Variables (Endpoints): Described in table below

- Population-level summary (estimate of the treatment effect): Described in table below

Assessment	Variables (Endpoints)
Spontaneous pain as assessed by the spontaneous NRS score	Change from baseline in the spontaneous NRS score to each scheduled timepoint
Stimulus evoked pain as assessed by the NRS score during QST	Change from baseline in the stimulus evoked NRS score to each scheduled timepoint

Spontaneous NRS Score

For each visit, spontaneous NRS (average and worst pain) score is assessed twice per day. The 2 assessments will be described separately as well as the daily average (mean of the NRS score assessed in the morning and in the evening) for the average NRS and the daily worst value for the worst NRS scores (worst NRS score assessed by day).

Baseline will be derived as defined in section 5.1.3.

To support the analyses of NRS score, the following endpoints will be considered:

- Time weighted Sum Pain Intensity Differences (SPID) from time 0 to each visit:

$SPID_{0-wx} = \sum_{i=0}^{i=n} CHG_i (t_{i+1} - t_i)$ where t_0 is the baseline time, t_i is the scheduled assessment time and CHG_i is the change from baseline in pain intensity at each post-dose scheduled timepoint.

- Sum Pain Intensity Differences Area Calculation (Area Under the Effect (AUE)):

$AUE_{0-wx} = \sum_{i=0}^{i=n} (CHG_i + CHG_{i+1})/2 * (t_{i+1} - t_i)$ where t_0 is the baseline, t_i is the scheduled assessment time and CHG_i is the change from baseline in pain intensity at each post-dose scheduled timepoint.

SPID and AUE will be evaluated at each visit (Week 6, Week 12 and end of study) using the worst pain within the last 12 hours and using the average pain within the last 12 hours, based on the spontaneous NRS score.

Painful Area Mapping

Painful area mapping includes longitudinal axis (cm) and total painful area (cm^2). It is assessed at screening, injection test 1 and 2, baseline, day 1 pre-dose, week 6, week 12 and end of study. Change from baseline will be derived for each parameter.

QST

The stimulus evoked NRS score is assessed during QST at baseline (day -7 day -1), week 6 and week 12, and include the following parameters:

- **Baseline assessment** on contralateral/non-painful area on painful area: NRS assessment is performed on each area (baseline assessments).

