For each subject, the number of incorrect perception of temperature by test will be derived for the painful and non-painful area.

Temperatures below or equal to 0°C and temperatures above or equal to 50°C are not reliable for the analyses and therefore will be excluded from the statistical analyses.

5.7.4.2 *Main Secondary Analysis*

For each estimate, analysis will be based on the treatment policy estimand: No adjustment will be made in case of intake of rescue medication.

Painful Area Mapping

Summary table for raw data and changes from baseline of the longitudinal axis and the total painful area will be provided by treatment group and measurement time and Placebo versus all Dysport groups by measurement time.

Spontaneous NRS scores

Each analysis on the spontaneous NRS score will be produced separately for the Average Numeric Pain Rating and the Worst Numeric Pain Rating.

Summary table for raw data and changes from baseline in the spontaneous NRS score will be produced by treatment group, and measurement times, only for the daily average for the average NRS scores and for the daily worst for the worst NRS scores).

The graph of arithmetic mean \pm SD over time will be provided for the change from baseline in the spontaneous NRS score (daily average for the average NRS and the daily worst for the worst NRS) with all treatment groups on the same graph. Size groups at each time point will also be presented on the graph.

The graph of arithmetic mean \pm SD over time will be provided for the change from baseline for the morning score and evening score on the same graph, separately for each treatment group.

Individual raw data and change from baseline spontaneous NRS score versus time profiles will be presented graphically for each subject with the worst numeric pain rating within the last 12 hours and the average numeric pain rating within the last 12 hours on the same graph.

Listings of individual data of the spontaneous NRS scores will be provided including all subjects with missing data. Values measured on a day where a rescue medication was taken will be flagged.

Summary table for SPID and AUE parameters will be computed for each assessment, by treatment group and visit.

For each assessment, scatter plots and box whisker plots will be generated for the comparison of SPID and AUE between the treatment groups.

Listing of individuals values of SPID and AUE will be provided.

OST analyses

Baseline assessments

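### Each by-timepoint NRS change rests on one diary day set against a baseline of up to seven days; the SAP should define the timepoint and use a 7-day mean for the by-visit table

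*Protocol*

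**What the plan says.** Protocol 9.1.3 has the Actiwatch "alert the subjects twice a day to record their average and maximal NRS scores over the preceding 12 hours", from the training visit to the end of study. Protocol 3.2.2 lists "Change from baseline in the spontaneous NRS score to each scheduled timepoint" as a secondary endpoint. Protocol 11.3.3.2, Table 4, gives the estimate for the placebo comparison: "Difference between each Dysport doses and the placebo group, in the mean change from baseline in the spontaneous NRS score to each scheduled timepoint". No averaging window is stated in either place.

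The two sides of the change are built differently in the SAP.

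- **Baseline (SAP 5.1.3):** for spontaneous NRS, "baseline will be defined as the mean of all pre-dose data (from day -7 and including pre-dose on Day 1".
- **Post-dose (SAP 5.7.4.1):** for average pain, the "mean of the NRS score assessed in the morning and in the evening" of one day; for worst pain, the worst score of that day.
- **Change table (SAP 5.7.4.2):** produced "only for the daily average for the average NRS scores and for the daily worst for the worst NRS scores".

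On timing, SAP 5.1.1.3 says "Summaries by visit will be presented using visit number as collected in the electronic Case Report Form (eCRF" and lists Day 1, Days 2 to 7 under one label, then every second week from Week 2 to Week 14, and end of study. Visits and calls may move by three days either way (Protocol 5.2.3.2, SAP 6.1). Weeks 2, 4, 8, 10 and 14 are telephone calls (Protocol 18.1).

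On missing data, SAP 5.7.1.2 refers to the relevant sections, but SAP 5.7.4 contains no rule. SAP 5.7.4.3 plans no sensitivity analysis, and SAP 2.6 drops the missing-data analyses foreseen in the protocol.

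**The concern.** A mean over several days is subtracted from a one-day value. The day-to-day fluctuation of the post-dose day enters the change almost undamped, although the entries of neighbouring days are already in the database. The secondary efficacy objective is the comparison of each dose with placebo. No test is planned, so the precision of this descriptive difference is most of what it can offer. In arms of six, avoidable noise is worth removing.

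Two gaps add to this. With a visit window of plus or minus three days, and with several timepoints being calls, up to seven diary days could be taken as the visit day, and the choice is left to the programmer. If the chosen day has no entries, the subject has no value at that timepoint: one of six, or 17% of the arm. What happens when only one of the two entries is present is not stated.

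**Working it through.** **The plan's own figure.** There is no power calculation, SD or effect size to reproduce. The arm size follows from the 3:1:3:1:3:1 ratio: 24 × 3/12 = 6 per Dysport dose, and 3 × (24 × 1/12) = 6 on placebo.

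**Entries that reach the change table.** Two entries a day give 14 a week and 16 × 14 = 224 over 16 weeks.

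- *Timepoint means visit.* In a visit week 2 of 14 entries are used. Visits are two-weekly, so per fortnight 26 of 28 stay out of the table. Eight visit days (16 entries) plus Days 2 to 7 taken daily (12) make 28, so 224 − 28 = 196 (87.5%) stay out.
- *Timepoint means diary day.* No entry is left out, but each timepoint still rests on one day.

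**Precision.** All variance inputs below are assumptions, because the documents give none.

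Var(change) = σ_b² + Var(baseline mean) + Var(post-dose mean)

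Here σ_b is the between-subject SD of true change. SE(difference) = √(2 × Var/6), and the 95% half-width is t(0.975, 10 df) × SE with t = 2.228. The baseline is taken as the full 14 entries.

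*Central case:* entry SD 1.0, correlation 0.5 between successive entries decaying geometrically, σ_b 1.5.

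- Variance of a 2-entry mean: (1 + 0.5)/2 = 0.75.
- Variance of a 14-entry mean: [14 + 2 Σ(14 − k) 0.5^k]/196 = (14 + 24.0)/196 = 0.194.
- One day: 2.25 + 0.194 + 0.75 = 3.19, SD 1.79, half-width 2.30.
- Seven days: 2.25 + 0.194 + 0.194 = 2.64, SD 1.62, half-width 2.09.
- The variance falls by 17%, equivalent to 6 × 3.19/2.64 ≈ 7.3 subjects per arm.

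*Second model:* a day effect, correlated between days (ρ), plus independent error for each entry. The grid was σ_b 1.0 to 2.5; day SD and entry SD (0.5, 0.5), (1.0, 0.7) or (1.5, 1.0); ρ 0 to 0.8.

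| σ_b | day SD | entry SD | ρ | SE, one day | SE, 7 days | reduction |
|---|---|---|---|---|---|---|
| 2.5 | 0.5 | 0.5 | 0.8 | 1.51 | 1.48 | 1% |
| 1.5 | 1.0 | 0.7 | 0.3 | 1.12 | 0.97 | 14% |
| 1.0 | 1.5 | 1.0 | 0 | 1.18 | 0.77 | 34% |

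The first and last rows are the extremes of the grid. If Actiwatch training falls later than Day −7, the baseline has fewer entries. That adds the same variance to both columns and makes the relative gain smaller.

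**Worst pain.** The post-dose value is the higher of two entries; the baseline is a mean of all entries. With normal entries, the expected excess of the higher of two over their mean is SD × √((1 − correlation)/π). In the central case this is 1.0 × √(0.5/π) = 0.40 points. A subject with no change would appear about 0.4 points worse. The shift should largely cancel in the difference from placebo, but it distorts the change within each arm. The precision figures above model means of entries, so they apply to average pain and not directly to the daily worst score.

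**The case against.** A reader might infer that most of the diary is wasted, at 12 of every 14 entries. The documents do not support that. SPID and AUE, which SAP 5.7.4.1 adds in support of this same NRS analysis, accumulate change over the assessment times. The SAP also plans mean-over-time graphs, individual profiles and listings. The exclusion concerns the change table alone, and only if timepoint means visit. SAP 5.7.4.1 and the visit list favour that reading without settling it. SPID and AUE do not replace the table: they run from time 0 to Week 6, Week 12 and end of study, so they do not give the change at a given week.

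A reader might also infer a loss of power. No test or power calculation is planned; what is lost is precision of a descriptive estimate. The gain may be negligible, and in the central case both half-widths exceed the two points that the protocol uses to define onset. That stands, and it limits the importance of the point.

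On missing days, the protocol provides a paper back-up diary and calls that check compliance with pain assessments. These make a lost day less likely, but they do not supply a rule for one.

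Finally, a weekly mean assumes that the effect is roughly steady over the week. In a study meant to describe time course, averaging can blur the by-visit value while the effect is changing. This is a real cost, which the daily profiles limit.

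**Conclusion.** The point holds in a limited form. Each by-timepoint change sets a one-day value against a baseline of up to seven days, whichever meaning of timepoint is intended. The SAP defines neither the diary day that represents a visit nor the handling of a missing day. If timepoint means visit, the Dysport-placebo difference in the change table is noisier than the collected data allow.

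The size cannot be computed from the documents. Under the assumed values, a 7-day mean lowers the standard error by roughly 1% to 34%, and little is gained if between-subject variation dominates. Arms of six stay imprecise either way. The point concerns the secondary change endpoint, not the derivation of onset, peak or duration. The change is worth making because it is cheap and because the definition is needed in any case.

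**What to change.** In SAP 5.7.4.1 and 5.7.4.2:

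- State what a scheduled timepoint means for diary NRS.
- For Week 2 to Week 16, define the by-visit value as the mean of the available daily values over the 7 days up to the visit or call, with a minimum number of days (for example 4). Below that minimum the value is missing.
- State how a day with only one entry is treated.
- For worst pain, use the mean of daily worst scores after dosing, and amend SAP 5.1.3 so that the worst-pain baseline is also built from daily worst scores.
- Keep Days 2 to 7 daily, and keep the daily graphs.

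The cost is SAP wording and programming; no new data are needed. The downside is some blurring of the by-visit value while the effect is changing, which the daily profiles still show.
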